## **WITHDRAWAL OF PARTICIPANTS**

There are minimal risks to be incurred from participating in this study. Specific risks related to the clinical and cognitive assessments (study questionnaires), visual stimulation are described below.

Participants will be reminded that they may stop participating in the study at any time for any reason with no penalty or loss of benefits to which they are otherwise entitled. Participants will be encouraged to take breaks when needed. They will be reminded that they may refuse to answer any questions on the study questionnaires, and they may stop the nociceptive stimulation session at any time.

During arousal experiments, since the risk of adverse medical effect is extremely low and participants inclusion criterion bars participants with sensitivity to visual stimulation, any adverse effects will be dealt with through usual emergency procedures (calling 911).

Syncpe, vasovagal response, signs of seizure, and verbal complaints of dizziness and vertigo will be considered as criteria for terminating the experiment. The Project Coordinator on site will be responsible for reporting all events to the PI and Safety Officer within a day, and these events will then be reported to the NIH and IRB according to the following scheme:

- Unanticipated problems, complaints and serious adverse events will be reported to NIH and IRB within 5 days
- Unanticipated Adverse Device Events and Major deviations within 10 days.
- Minor deviations will be aggregated and reported with continuing review or study closure.

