### ***Adverse Events associated with Experiments 2***

We are concerned that pain induction and visual stimulation each has the potential for creating adverse effects, although they are unlikely to occur. CHEPs stimulation is commonly used pain-induction models for experimental purposes. It has been well described and are known to have a very low potential for harm to study volunteers because the stimuli can be precisely controlled. Within the individually predetermined range of nociceptive stimulation, participants are expected to experience neither psychological distress nor tissue injury. The latter will be verified by study personnel through inspection of the involved skin after the first test stimuli are administered (during the initial demonstration of study procedures to participants) as well as after all nociceptive stimulation has concluded. Furthermore, the study team members involved in pain induction will be present throughout and observe the participants directly during the entire process. In the highly unlikely event of equipment malfunction or misapplication, both of which

would trigger the need for reporting, arrangements will be made for participants to be evaluated by the on-site physician as stipulated in the protocol.

With regard to pain stimuli, adverse events are:

- excessive intensity of induced pain, defined as 80-100mm on VAS,
- anxiety/fear, defined as a 100% increase (i.e., doubling) in heart rate or >135 beats per minute, and
- injury to skin, likely in the form of a burn, defined as skin discoloration (i.e., red, white and/or brown) that does not resolve within 10 minutes of stimulus discontinuation.

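### Experiment 2 defines numeric pain and heart-rate limits as adverse events, but neither is a termination criterion and no pause, stop, step-down or evaluation rule is attached to them

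*Combined protocol and SAP*

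**What the plan says.** The section on adverse events for Experiment 2 sets two limits that can be met while the blocks are running: "excessive intensity of induced pain, defined as 80-100mm on VAS" and "anxiety/fear, defined as a 100% increase (i.e., doubling) in heart rate or >135 beats per minute". It does not name the baseline from which a doubling is measured. A third event, skin injury, is defined by discoloration "that does not resolve within 10 minutes of stimulus discontinuation".

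The section on withdrawal of participants gives the only termination rule: "Syncpe, vasovagal response, signs of seizure, and verbal complaints of dizziness and vertigo will be considered as criteria for terminating the experiment". It then makes the site coordinator report all events to the principal investigator and the safety officer within a day, with onward reporting to the NIH and the IRB.

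Other safeguards are stated:
- Pain levels are set by a step method before the blocks (Experiment 2, Experiment structure), and stimulation is described as "Within the individually predetermined range of nociceptive stimulation".
- Staff involved in pain induction stay and watch throughout (adverse events, Experiment 2).
- Participants are told that "they may stop the nociceptive stimulation session at any time", and are encouraged to pause when they need to (withdrawal section).
- People with cardiac disorders are excluded (exclusion criteria; risks section).
- The principal investigator monitors safety (data and safety monitoring section).
- Physician evaluation is arranged "In the highly unlikely event of equipment malfunction or misapplication".

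**The concern.** The sponsor has decided what counts as excessive pain and as an anxiety response, and has put numbers on both. The termination rule then leaves both out. Staff who follow the written rule could go on delivering nociceptive stimuli after a rating of 80 mm or more, or a heart rate past the limit. Stopping would rest with the participant or with unstated staff judgement.

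The participants are healthy volunteers who gain no direct benefit. The heart-rate limit matters here because Experiment 2 pairs pain with visual stimuli intended to raise arousal, while the step method checks pain levels and not heart-rate response.

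There is also a data issue. Without a rule, two members of staff may respond differently to the same reading, so VAS ratings would be lost inconsistently.

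**Working it through.** The plan gives no event rate or stopping figure to reproduce. The check is a comparison of texts, with simple counts for exposure and timing.

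**1. Adverse-event definitions against the termination list**
- Visual-stimulus events (Experiment 1): seizure, dizziness or vertigo, syncope. All 3 of 3 are in the termination list.
- Pain-stimulus events (Experiment 2): high VAS, high heart rate, skin injury. 0 of 3 are in the list.
- The list adds only vasovagal response to the Experiment 1 events.

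The list therefore largely carries over the Experiment 1 events.

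**2. Whether another provision supplies the missing action**

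| Provision | Refers to a high VAS or heart rate? | Tells staff what to do during the session? |
|---|---|---|
| Step method and individual range | No | No; lowers the chance of an event |
| Staff observation | No | Watch; no response stated |
| Breaks and right to stop | No | No; the decision is the participant's |
| Cardiac exclusion | No | No; applies at entry |
| Principal investigator's monitoring | No | No |
| Reporting within a day | Yes, if all events is read naturally | Report; no immediate step |
| Physician evaluation | No; equipment malfunction or misapplication | Not for these limits |
| Emergency call | No; introduced for the arousal experiments | Not for these limits |

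No row gives a pause, stop, reduction or medical evaluation tied to either limit.

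**3. Exposure after a limit is reached**
- Inputs (Experiment 2, Experiment structure and Block structure): 12 blocks, 8 trials per block, 4 minutes per block, 45-second breaks.
- Trials: 12 × 8 = 96. If a limit is reached on trial k, 96 − k remain; for k = 1 that is 95.
- Duration: 12 × 4 + 11 × 0.75 = 56.25 minutes.
- Up to three temperature levels are planned and the share of each is not stated. Assuming equal shares, hot trials would number 96/3 = 32 with three levels, 96/2 = 48 with two, or 96 with one.

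**4. Whether a pause before the next stimulus is feasible**
- Inputs (Approximate trial structure, Experiment 2): heat starts 2 to 5 s into the trial and lasts up to 0.8 s; the rating window runs from 15.5 to 30 s.
- Latest end of heat: 5 + 0.8 = 5.8 s, before the rating opens. A rule cannot undo the stimulus that was rated; it can prevent the next one.
- Earliest next heat: 30 + 2 = 32 s. The gap after the rating window closes is at least 32 − 30 = 2 s, and 45 s longer across a break.
- The VAS is computerized and the thermode is software-controlled, so an automatic hold fits this gap. ECG is recorded, but no live heart-rate alert is described.

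**The case against.** An adverse-event definition says what is recorded; it need not be a stopping rule. The VAS is the participant's own report, and the person who rates 80 mm is the person who has been told they may stop. The stimulus is brief and over before it is rated. Calibration, the cardiac exclusion, breaks on request and staff presence all lower the risk. A stop triggered by VAS also removes values of the very outcome used to judge success, in an experiment of 20 participants.

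Much of this stands. The safeguards are real, and outcome-dependent loss is a true cost. But the plan does state a termination rule, and these two limits are absent from it. Calibration makes an event less likely without saying what follows when one occurs. Leaving the decision to the participant does not help with heart rate, which the participant does not report.

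A reader might infer that no staff action of any kind is tied to the limits. The text does not support that: the one-day duty to report all events, read naturally, covers them, although it could be read as covering only the termination events just before it. A reader might also infer that staff are told to continue past a limit. They are not; the plan is silent.

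Nor does the text show that a skin-injury limit would be passed unnoticed from trial to trial. That definition needs a 10-minute wait, and skin is inspected after the first test stimuli "as well as after all nociceptive stimulation has concluded".

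**Conclusion.** The concern holds in this form: the pain and heart-rate limits are not termination criteria, and beyond observation, monitoring, breaks, the participant's right to stop and reporting within a day, no supplied text tells staff to pause, stop, reduce the stimulus or seek medical evaluation when either is reached. It should be fixed, because the gap concerns participant safety and a remedy is cheap.

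The size that can be stated is exposure, not harm: up to 95 of 96 trials could follow a limit reached on the first. The number that would be hot depends on an unstated mix of temperatures. How often either limit would be reached cannot be derived from the documents.

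Confidence is high for the comparison of the supplied text. The public copy omits some pages and refers to site-specific protocols that are not included, so a rule could exist there.

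**What to change.** Add to the withdrawal section:
- A VAS rating of 80 mm or more, or a heart rate above 135 bpm or doubled from a resting value recorded before the first pain stimulus, requires staff to pause nociceptive stimulation before the next stimulus.
- Stimulation ends for that session if the event recurs or does not settle within a time that the sponsor states.
- The rule applies identically in every stimulation condition.

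The resting value needs its own line: sensors are set up and calibrated before the step method, but the plan does not say that a resting heart rate is recorded then.

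For the analysis, keep ratings already collected, and report pauses, stops and lost ratings by condition. If the temperature is lowered for safety, report later ratings separately and do not pool them with earlier ones.

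The cost is a short amendment, a hold in the session software, and a heart-rate display or alert built on the ECG already recorded. Some sessions will be shorter; the number is unknown. Some VAS ratings will be lost in a way that depends on the outcome and could differ by condition. If the visual stimulation works as hypothesized, pain stops would be fewer with it and heart-rate stops might be more frequent. Reporting by condition makes that loss visible but does not remove it.

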## **RISKS TO PARTICIPANTS\***

The potential risks of this experiment are extremely low. Given mild inconvenience of the CHEPs stimulation we are excluding volunteers with cardiac, neurologic, endocrine, gastrointestinal or renal disease or chronic pain conditions, as well as those with a history of prior major surgery. In addition, the participants will be exposed to visual stimulation which could potentially induce seizures in individuals with heightened light sensitivity. Hence such participants will also be excluded from our study.

## **POTENTIAL BENEFITS TO PARTICIPANTS**

There is no direct benefit of this research to the study participants. The potential benefit of the research is to society in general, through the future development of a safe, effective, and affordable treatment for pain.

## **VULNERABLE POPULATIONS**

No vulnerable population is expected to participate in the study.

## **MULTI-SITE RESEARCH**

The research will be conducted at the Dandelion Science research facilities in Hoboken, NJ.

## **COMMUNITY-BASED PARTICIPATORY RESEARCH**

This type of research is not part of our experimental design

## **SHARING OF RESULTS WITH PARTICIPANTS**

There is a potential for observing abnormalities in our biosensor recordings. For example, with EEG recordings, we can observe signs of focal and general epileptiform and non-epileptiform waveforms; with ECG, we can observe arrhythmias, ischemia, and conduction abnormalities; and with EMG, we can observe radicular abnormalities and/or metabolic-related conduction disorders. Given that records are not performed for diagnostic purposes, if abnormalities are suspected the participant will be informed that such an abnormality was observed and instructed to follow up with their health provider for further investigations.

# SETTING

## Dandelion Science facilities

[figure not shown]
[figure not shown]
### *Laboratory*

[figure not shown]
Dandelion Science Corp

[figure not shown]
[figure not shown]
Dandelion Science maintains its primary office at this location. At this location Dandelion Science maintains space for overall company management, as well as areas appropriate for computer research and computer programming activities. Dandelion Science maintains Internet access and wireless networking capabilities, computer workstations where software developers will be clustered together, beta testing rooms, conference rooms for privacy and larger meetings, video conferencing capabilities, as well as other standard office provisions. Dandelion Science will perform all programming and product development activities on secure company-owned computers.

## **PRIOR APPROVALS**

The research will be funded through a NIH grant.

## **CONFIDENTIALITY**

Participation in this research will be kept confidential. In compliance with HIPAA protocols, all presentations of data will be void of unique identifiers in order to ensure that participant confidentiality is maintained. The experiment preparation will be conducted in a dedicated room with only the participants, the experimenter and the assistants present. In the beginning of the experimental setup a participant will be requested to sign a consent form, in which the experimental procedures and their rights as participants will be explained. The participants will be asked to provide general demographic information consisting of their age, gender and race/ethnicity. During the setup the electrodes will be attached to the participant's head, face, hands and palms, so participants will not be required to disrobe. The experiment will be conducted in a separate experimental booth, in which the participant will either be alone or with the experimenter depending on the specific details of the experiment.

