## GOALS

We are researching a novel neuromodulatory platform using visual stimulation for its impact on nociception. We hypothesize that short abstract videos can be optimized to be used in the modulation of nociception utilizing the process called Dynamic Visual Neuromodulation (DVN). DVN optimization will be performed through an iterative process of choosing different arrangements of concurrent stimulation parameters in order to enhance neurophysiological response. Since pain experiments are challenging, DVN optimization has been designed to be carried out in two stages in order to decrease the burden on participants: (1) In Experiment 1 we aim to develop an optimization procedure for inducing arousal; this experiment requires no pain induction. (2) Using the same general procedure, the Experiment 2 will pursue further optimization of the visual stimuli with the aim of inducing arousal to decrease nociception and the perception of experimentally induced pain in healthy subjects.

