### ***Adverse Events associated with Experiment 1***

Regarding the visual stimuli, adverse events are:

- seizure, defined as jerking movements of the limbs and/or loss of consciousness,
- dizziness/vertigo as defined by verbal complaints and loss of balance, and syncope.

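### Experiment 1 is to be ended on signs of seizure or syncope, yet the protocol lets the participant be alone in the booth and commits to direct observation only for pain induction

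*Combined protocol and SAP*

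**What the plan says.** Five sections of the combined protocol and SAP, and its opening Goals, bear on the point.

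- **Risks to Participants** says that participants will be exposed to "visual stimulation which could potentially induce seizures in individuals with heightened light sensitivity", and excludes such people for that reason.
- **Adverse Events associated with Experiment 1** lists "seizure, defined as jerking movements of the limbs and/or loss of consciousness", then dizziness or vertigo (recognised from complaints and loss of balance) and syncope.
- **Withdrawal of Participants** names syncope, a vasovagal response, "signs of seizure, and verbal complaints of dizziness and vertigo will be considered as criteria for terminating the experiment". For the arousal experiments, the stated response to an adverse effect is the usual emergency call to 911.
- **Confidentiality** has the participant prepared in a room with the experimenter and assistants, and then tested in a separate booth "in which the participant will either be alone or with the experimenter depending on the specific details of the experiment". It does not say which arrangement applies to which experiment.
- **Adverse Events associated with Experiments 2** says that "the study team members involved in pain induction will be present throughout and observe the participants directly during the entire process".
- **Goals** says of Experiment 1 that "this experiment requires no pain induction".

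**The concern.** A termination criterion based on a visible sign works only if someone is placed to see the sign. A participant who is convulsing or has fainted cannot report it, use the right to stop, or call for help. The protocol gives express permission for the participant to be alone, and its one promise of continuous observation is worded so that it does not reach the experiment in which most participants would be enrolled. At stake are whether the protocol's own termination criteria can be applied in Experiment 1, and whether a count of adverse events from it can be taken as complete.

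**Working it through.** The point turns on how the sections fit together. The arithmetic only sizes it.

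**1. Which criteria need an observer?** Set the Experiment 1 adverse events against the termination criteria:

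| Sign | Listed as Experiment 1 adverse event | Termination criterion | Can the participant report it at the time? |
|---|---|---|---|
| Seizure (limb jerking, loss of consciousness) | yes | yes | no |
| Syncope | yes | yes | no |
| Complaint of dizziness or vertigo | yes | yes | yes, if someone can hear |
| Loss of balance | yes | not named | possibly |

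The last column is my reading, not the protocol's. Two of the termination criteria, seizure and syncope, cannot depend on the participant speaking up.

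**2. Who is committed to watch?** The observation promise is limited twice: by its place (the Experiment 2 section) and by its subject (staff carrying out pain induction). Experiment 1 involves no pain induction. The one exception is a cold pressor pilot of up to 5 people described under Experiment 1. Even if the promise is read to cover them, it does not cover the visual stimulation sessions.

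**3. Does anything else in the plan detect an event?**

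- *Exclusions.* The Exclusion Criteria and Risks to Participants keep out people with photosensitivity or epileptic seizures. Screening is by a medical history questionnaire. This lowers the expected frequency but is not detection.
- *EEG.* The safety monitoring section says that recordings may show epileptiform waveforms. The only action attached, under Sharing of Results with Participants, is to tell the participant and advise follow-up with their own provider. No live review and no link to stopping is stated.
- *Response monitoring.* Responses are followed while stimuli are shown (Optimization method), and each trial ends with a behavioral response of 5 to 15 seconds. This serves the choice of the next stimulus parameters. No action on a missing response is stated.
- *Equipment.* No available text mentions a window, camera, intercom or call button.

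**4. Size.**

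- Share of participants: 100 / 120 = 83%. Both figures are ceilings.
- Blocks and breaks per Experiment 1 session: 25 × 3 min = 75 min of blocks, plus 24 × 0.75 min = 18 min of breaks, 93 min in all.
- Stimulation time within that, assuming blocks consist only of trials: a trial has 1 s of fixation, 5 to 15 s of stimulation and 5 to 15 s of response. The stimulation share runs from 5 / (1 + 5 + 15) = 5/21 to 15 / (1 + 15 + 5) = 15/21. Of 75 block minutes, that is 75 × 5/21 = 17.9 min to 75 × 15/21 = 53.6 min.

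The stimulation exposure is therefore roughly 18 to 54 minutes per session, not 93.

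**The case against.** The strongest reply is that alone in the booth is not the same as unobserved. The Confidentiality section says who is inside the booth, not whether anyone looks in from outside. Making signs of seizure a termination criterion, and placing a Project Coordinator on site, suggest that the authors assumed staff would notice. The setting figures and some text after the laboratory description were not available to this review, so the layout cannot be checked. This stands: a reader might infer that participants will go unwatched, and the documents do not show that. What remains is that the available text nowhere states the observation its criteria depend on, and expressly permits the arrangement that puts it in doubt.

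Second, the risk is small, since susceptible people are excluded and the protocol calls the risk extremely low. This stands as to frequency and tempers the point. It does not remove the need to detect an event that the protocol itself defines and acts on.

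Third, a reader might see a flat contradiction within Experiment 2, between staff present throughout and a participant who may be alone. The Confidentiality wording leaves the matter to the details of each experiment, and the Experiment 2 section can be read as supplying that detail. A cross-reference would settle it.

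Fourth, it is tempting to add that stimulation would run on through an event, that the emergency call would be delayed and brief events missed, or that a clean Experiment 1 record could not justify taking the stimuli into Experiment 2. The first three presuppose that nobody is watching, which is not shown, and a participant who stopped responding might be noticed from the trial data. For the last, the protocol describes no safety gate between the experiments: stimuli move forward after optimization for arousal.

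**Conclusion.** The point holds as a gap between a stated permission and a stated termination rule. In Experiment 1, seizure and syncope must be noticed by someone else, the participant may be alone in the booth, and no available text extends the observation commitment to that experiment. It affects up to 100 of up to 120 participants, each with about 18 to 54 minutes of visual stimulation per session under the trial timings given.

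The conclusion assumes that the unavailable setting material contains no observation requirement; if it does, a cross-reference closes the point. It does not establish that any participant will be unobserved, that events will be missed, or that seizure is ranked above the other listed events, which the protocol does not do. It is more than a missing detail because an unconscious participant cannot trigger the rule, and it should be settled in the protocol text.

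**What to change.** Reconcile the two adverse event sections, Withdrawal of Participants and Confidentiality. The protocol already holds the wording needed: extend the observation commitment in the Experiment 2 section to visual stimulation in both experiments. In Confidentiality, make clear that *alone* means alone in the booth but continuously observed by staff already running the session, and state the means for each experiment: in the room, by window or by live camera. The existing termination criteria stay as they are.

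The cost is a few sentences and, going by the text, no added staff. If a window or camera is already in use, one sentence recording it is enough; if not, out-of-room observation would need one. The small downside is that an observer in the room may affect arousal, which Experiment 1 sets out to measure. Observing from outside the participant's view limits that.
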